With a pre-randomisation design, a setting is created that reflects the future practice the most. This way, an impression can be received of the acceptance rate of the MRI examination.

3) The disadvantages for and burden on the participants are negligible (requirement of *proportionality*).

The researchers are of the opinion that not informing the control group will not cause important adverse effects for or burden of these participants. Actually informing them means the participants are also informed of their risks they were not aware of until that moment. To the more than 20,000 women in the control group, no other screening method can be offered (of course except for the usual mammographic screening every 2 years) or a form of risk reduction, which probably triggers a lot of unrest.

To be able to answer our research question, we do not need any other information from the control group other than on the occurrence of breast tumours in between two screening rounds (interval cancers) or with later screening rounds or on mortality as a result of breast cancer. This data can be obtained by linking the screening data with the data from the Dutch Cancer Registry and Statistics Netherlands (CBS) as is done now routinely already as part of the evaluation of the Dutch population-based mammography screening program (1). This routine linkage is also described in the folder of the regular Dutch populationbased mammography screening program. In that same folder, it describes how the women can object to such use. The data of both study arms are pseudonymized before processing and saving.

The women who are randomised to the intervention group are informed of the study, but this takes place after randomisation. Due to the prerandomisation design, it is only possible to get permission to agree to the *result* of the randomisation. The researchers are of the opinion that the intervention group does not suffer any harm as a result thereof. After randomisation, the women invited for MRI receive an extensive information package on the study and its benefit-harm ratio.

Sampling frame

The study population consists of participants of the Dutch population-based mammography screening program aged between 50 and 75. They are from screening regions located in the operation area of the hospitals where the MRI examinations are carried out (see *Section 10. Organisation*). Women with >75% density and a negative mammographic screening (i.e. no reason for further diagnostic follow-up) are eligible for this.

Selection of participants, inclusion and exclusion criteria

The density is automatically quantified with the help of a full-automatic method developed for digital mammography(19). This result will be linked to the mammographic screening result. The women with extremely dense breasts and a negative screening result (BI-RADS 1 or BI-RADS 2) qualify for the study.

The reason to focus on women between the ages of 50 and 75 and not on younger women with very dense breasts, is because the first group has a higher risk of developing breast cancer, and because the infrastructure for screening in this group already exists, so the value of the MRI can be examined relatively easily. If we can show that MRI has an added value to women with very dense breasts, this will be an important indication for a potential future cost-effective strategy for women of 45 to 49 years old.

Women with contraindications for MRI cannot take part in the study. Examples of contraindications for contrast MRI are: allergy for gadolinium contrast media, presence of iron aneurysm clips, metal chips in the eye and pacemakers. Every participant fills out a safety questionnaire to find out if there are no contraindications to expose the participant to strong magnetic fields and/or contrast medium.

Randomisation and stratification

The DENSE trial applies the pre-randomisation design, whereby only the intervention group is informed about participation in the trial after randomisation (see paragraph 7.6 Research Method: design). Randomisation takes place if the breast density is extremely dense and a negative mammographic screening examination (BI-RADS mammography 1 or 2).

Randomisation takes place between:

Arm I (intervention): additional MRI examination

Arm II (control; Dutch guideline): no further examination until the following screening round 2 years later (unless there is reason to do a breast examination in the meantime, because of complaints by the participant for instance).

The participants are randomised by a computer-generated randomisation sequence, with stratification for screening centre. A screening centre is a radiologic partnership assessing the screening mammograms for a certain region.

Blinding

The proposed experimental population-based screening study is a pragmatic (in comparison to explanatory) trial whereby two different screening strategies, including possible placebo or external effects, are compared. The importance of blinding the outcome measure in a pragmatic trial depends on the 'hardness' with which the outcome measure can be determined. In this case, it concerns the presence of breast cancer (screening-detected and interval cancers), which will be assessed objectively with the help of histology. Thus, blinding in this trial is not necessary.

Starting and end date project Within this experimental population-based screening study, 3 screening rounds will be carried out in a period of 6 years. Because of the capacity at the MRI centres, it might be necessary to include the screening rounds in stages, we pursue a longer period for the entire study, namely from 1 September 2011 to 1 September 2019. However, the research period per participant is still 6 years. For every participant, the intervention in a following screening round is the same as in her first screening round, so independent of, for example, a possible change in breast density. Eventually sensitivity analysis will be carried out to find out whether this has possibly influenced the results.			
7. Sample siz	e, feasibility		
interval cance group. The as Team for Bre	size is calculated on a er percentage between ssumptions are based o east Cancer Screening kowske et al. (6) and a	the intervention gro on the report of the in the Netherland	oup and the control National Evaluation s 1990-2007 (1), a
screening exa between scree occurrence of extrapolation setting. The p detected tum	aged 49-50, there a aminations: 4.2/1000 b enings (interval cancer breast cancer in the c of the data collected by programme sensitivity ours divided by the r a screening interval o	y screening and 2/ s) (1). In the table k lifferent density cate Kerlikowske and e (calculated as the total of screen-de	1000 in the interval below, the expected egories is based on t al. (6) to the Dutch number of screen- tected and interval
Breast	Number of breast	•	Proportion
density	cancer diagnoses (screening + interval) per 1000 examinations*	Sensitivity (Scr / (Scr+Int))***	interval cancers (=1-Sensitivity)
total	6.2**		
<25%	2.5	82%	18%
<25% 25-50%	2.5 5.6	74%	26%
50-75%	7.6	66%	34%
>75%	8.0	45%	55%
from Kerlikowsl ** from the N Netherlands 19 *** calculated interval	rence of breast cancers ke et al. (6) for women of lational Evaluation Tea 90-2007 report (1) from the article from Va roup with >75% dens	50-69 years of age m for Breast Canco n Gils et al. (32) fo	er Screening in the or a 2-year screening
cancers per 1	000 mammographic so ion is that the MRI is	reening examinatio	ns is 4.4 (0.55*8.0).

stromal tissue, which is why women with >75% density can reach the same sensitivity using an MRI as with mammography among women with <25% dense tissue (i.e. 82%, see table). By adding MRI, we also expect that the proportion of interval cancers decreases to 1.44 per 1000 screening examinationss (0.18*8.0).

In the pre-randomisation design, it is necessary to take into account the fact that there are women who do not wish to take part after randomisation. Because this non-participation only occurs after randomisation, the non-participants must be included in the analysis according to the intention-to-treat principle. This means the required sample size becomes larger (35). A study by Berg et al. (23) on the added value of MRI in the ACRIN 6666 trial showed that 57.9% of the women contacted participated in the MRI substudy. For a number of women, money or not having insurance was the decisive factor. Without these reasons, the participation level would have been 66%. We expect to reach a participation of 66% because the cost of MRI examination is covered in our study.

In the intervention group, the expected interval cancer rate is 1.44/1000 screening examinations among the 66% who participated in the MRI examination and 4.4/1000 among the 33% that did not participate in the MRI examination. As a result, the interval cancer rate in the intervention group is 2.49/1000 screening examinations.

With a 1:4 ratio randomisation, 7,237 women are needed in the intervention group (of which 4,776 (66%) actually do take part in the MRI examination) and 28,948 women in the control group to show the difference between 4.4/1000 and 2.49/1000 as statistically significant (1-sided alpha=0.05) with a power of 80% after 1 screening round and the subsequent interval. This was calculated using the sample size software PASS.

Feasibility

The experimental population-based screening study will be integrated in the infrastructure of the Dutch population-based mammography screening program, which is national and entirely digital. We foresee to have to invite 7,237 women to be able to include 4,776 women (expected participation rate 66%) in the intervention group. The total study population (intervention and control group) will consist of 36,185 participants. The total target population of participants in the Dutch population-based mammography screening program with >75% density in the Netherlands is 90,000 in a period of 2 years, so we could expand our recruitment if the number of people participating is disappointing. We invite women living near the participating MRI centres (referred to in *Section 10. Organisation*). Every centre will have to make on average 400 extra MRI examinations per year for this experimental population-based screening study. The centres have already indicated their desire to participate.

8. Effectiveness of treatment and practice options

It is known that treating breast cancer in an early stage reduces the mortality rate. This is the motivation to conduct a population-based screening program on breast cancer in the Netherlands. The recently

updated meta-analysis from Nelson et al. (36) for the US Preventive Taskforce 2009 report confirms again that mammographic screening reduces the number of deaths due to breast cancer. The relative risk of dying because of breast cancer is lower among women invited for mammographic screening compared to women in a control group who are not invited for screening (50-59 years: 0.89 95%CI 0.75-0.99; 60-69 years: 0.68 95%CI 0.54-0.87). Furthermore, it is known that with mammographic screening, breast tumours among women with extremely dense breasts are diagnosed at a later stage compared to breast tumours among women with low density.
If we would be in the position to realise that same early detection among women with very dense breasts, it may be expected that this would reduce the number of deaths due to breast cancer. There are no indications thus far that breast tumours among women with very dense breasts have other intrinsic characteristics which would give them a more favourable or unfavourable prognosis (30;37).
9. Outcome analysis, evaluation
Indicators of screening effectiveness The extra number of tumours detected by MRI, but missed by mammography, shall be described as well as the recall rate, the positive predictive value (and the false positive percentages) of the MRI and the number of biopsies per positive MRI test, with the corresponding 95% confidence intervals.
The primary outcome is the comparison of the interval cancer proportions between the study groups (Chi-square or Fisher's exact test in case of small numbers). Tumour size, stage and degree of the tumours will be compared between the arms as well as the distribution of histological and molecular subtypes. With respect to tumour size, the difference between means will be tested using the Student's T-test. If not normally distributed, the medians will be calculated and the differences will be tested using the Mann-Whitney U test. Differences in stages, grade, histological and molecular subtypes are tested using Chi-square or Fisher's exact test in case of small numbers.
A problem already mentioned before, with the single consent version of the pre-randomisation design, is the dilution of the effect by non-participation in the intervention group after randomisation. Nevertheless, to be able to reach a true (nondiluted) estimation of the effect of the MRI, the analysis method of Cuzick et al. (35) will be used, which was specifically designed for these kinds of screening studies.
Estimation of mortality reduction Calculating the actual mortality reduction requires a very long follow-up period and an even larger study population than proposed here. Breast cancer screening simulation models are a less expensive and faster approach to study the mortality reduction rate of this intervention. We use the MISCAN simulation programme that was specifically designed to build cancer screening models and also to analyse and explain the cancer

screening trial results such as these, and to compare the cost-effectiveness of different screening measures (38;39). It is a validated model that has been applied numerous of times successfully in evaluating different screening strategies. It is also one of the most commonly used breast cancer models by the Cancer Intervention and Surveillance Modelling Network (CISNET) consortium sponsored by the National Cancer Institute (40). In MISCAN, the individual life courses are generated as a Markov process of stages and transitions. For this, the characteristics of the study population (demographic data, risk factors) are fed to the model. The results of the screening and the scenarios as applied in the proposed experimental population-based screening study are estimated for a cohort of 1 million women with very dense breasts. The effects on mortality and life vears gained with the different screening scenarios are estimated at a period of 10 years after the start of the screening. The most important parameters in the model are the average duration of the preclinical stages that can be detected with screening, sensitivity of the screening test and improvement in prognosis after detection through screening. Outcomes of the model are the number of screen-detected tumours and interval cancers (including stage distribution), age-specific breast cancer incidence, stratified by stage, and age-specific breast cancer mortality.

Analysis of cost-effectiveness

The breast cancer simulation model will also be used to predict the costs and effects of different screening strategies for a situation in which the screening is carried out for 10 years. The costs of the diagnosis and treatment of breast cancer will be registered as part of the experimental population-based screening study. Costs and effects are calculated for a simulated cohort of 1 million women for a period of 10 years after the start of the screening. The costs are presented in euros. The effects are presented in terms of breast cancer mortality reduction and number of life years gained. Cost-effectiveness ratios (CER) are expressed in costs per life-year gained and incremental cost-effectiveness ratios (ICER) as extra costs per extra life-year gained. For the intervention group, the guality of life is assessed using the EuroQoI-5D questionnaire. To estimate the number of guality-adjusted life years of the control group, we use the EuroQol-5D health status data of the general population of Dutch women of the age between 50 and 75 (41). We implement weighting factors with a reduction of 10%, 25%, 40% for respectively non-metastatic tumours, tumours with metastases in the regional lymph nodes or tumours with distant metastases. For this reason, the ICER is expressed in extra costs per quality adjusted life-year gained.

Analysis of quality of life

The effect of MRI screening on the quality of life of the women will be assessed using questionnaires. The EuroQoI-5D questionnaire is a validated and a frequently-used questionnaire that is able to assess the quality of life with a few short questions, regarding physical as well as psychological consequences (41).

In addition, the psychological consequences the experimental populationbased screening study could cause will also get attention by using the 'Consequences of Screening---Breast Cancer' (COS-BC) questionnaire (42). The first part of the questionnaire (COS-BC-1) asks specifically about the fears and uncertainties during the screening procedure. The second part of the questionnaire (COS-BC-2) aims to get the woman to look back at the entire period of examinations and have her assess whether it has brought about positive and/or negative changes. The great advantage of the COS-BC questionnaire in comparison to other validated anxiety questionnaires is the fact that it is focussed specifically on breast cancer screening. With three short questions, the screen-specific items questionnaire uncover the burden experienced by the MRI examination (43). The group of women with MRI-detected breast cancer will be asked to answer the EORTC questionnaire once (44). The goal of the quality of life analysis is to investigate the (changing) quality of life in the intervention arm as a whole. Besides, whether differences can be observed between participants with false positive, true positive, false negative and true negative MRI results will be addressed. The moments at which time the different questionnaires are conducted is indicated in the flowchart (see 'Flowchart timing of questionnaires'). Interim analyses The first analyses are carried out after the first screening round, namely: 1. When all women in the intervention group have received an MRI, including any possible diagnostic work-up. At that point, the extra number of tumours detected by the MRI, and missed by the mammography, can be estimated, as well as the recall rate, the positive predictive value and the number of biopsies per positive MRI test. 2. Two years after the last participant has been screened, the difference in the proportion of interval cancers is analysed and the tumour size and stage between both groups are compared. An interim analysis on the primary outcome is not possible, because information on interval cancers is only available after all participants have been screened and followed for two years. For the false-positive percentage, interim monitoring will take place. From the abstract from Berg et al. (23) on the added value of MRI in the ACRIN 6666 trial, it is possible to calculate that the percentage 'unjustified' referrals in the entire investigated group is 17% and the percentage 'unjustified' biopsies is 9%. Based on this, we have decided the following: If after the first 750 MRI examinations the number of unjustified referrals is more than 25% or the number of unjustified biopsies is above 15%, consultation on modification of the intervention in relation to the referral criteria is necessary and suspending the trial could be considered. A Data Safety and Monitoring Board is installed to this end, in any case consisting of an independent biostatistician, radiologist and oncologist as its members.

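### The diluted intervention-arm rate of 2.49 per 1000 in the power statement does not follow from the plan's inputs, which give 2.446 per 1000

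*Combined protocol and SAP*

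**What the plan says.** All the inputs are in Part 7, section 7.

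- Among women who have the MRI, the plan expects that "the proportion of interval cancers decreases to 1.44 per 1000 screening examinationss (0.18*8.0"). The control rate is 4.4 per 1000 (0.55 × 8.0).
- On uptake: "We expect to reach a participation of 66% because the cost of MRI examination is covered in our study".
- The two rates are then mixed: "1.44/1000 screening examinations among the 66% who participated in the MRI examination and 4.4/1000 among the 33% that did not participate". The result is "As a result, the interval cancer rate in the intervention group is 2.49/1000 screening examinations".
- The power sentence states that, at 1:4 allocation, "7,237 women are needed in the intervention group (of which 4,776 (66%) actually do take part in the MRI examination") and 28,948 controls are needed to show "the difference between 4.4/1000 and 2.49/1000 as statistically significant (1-sided alpha=0.05) with a power of 80% after 1 screening round" and the interval after it.
- On method the plan says only: "This was calculated using the sample size software PASS".
- The feasibility text repeats the head counts: "We foresee to have to invite 7,237 women to be able to include 4,776 women (expected participation rate 66%) in the intervention group".

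**The concern.** The diluted rate is a weighted average of two stated rates with a stated weight, so anyone can check it, and the printed value does not come out. The weights as printed do not sum to 100% either. The rate is not background: it is the detectable effect in the plan's only power statement, which concerns the primary outcome. A reader who enters 4.4 and 2.49 per 1000 into the formula that matches the planned chi-square test will conclude that the trial is several hundred intervention women short. A reader who starts from 66% participation will find that it is not. The plan should not support both conclusions.

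**Working it through.** **Inputs (all from Part 7, section 7).** Control rate 4.4 per 1000; rate in MRI participants 1.44 per 1000; participation 66%; 7,237 intervention women, of whom 4,776 take part; 28,948 controls; one-sided alpha 0.05; power 80%.

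**1. The diluted rate.** Rate = p × 1.44 + (1 − p) × 4.4, where p is participation.

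| Weights | Calculation | Rate per 1000 |
|---|---|---|
| 66% / 34% | 0.9504 + 1.4960 | 2.4464 |
| 66% / 33%, as printed | 0.9504 + 1.4520 | 2.4024 |
| 66 / 33 rescaled to 100% | 2.4024 / 0.99 | 2.427 |
| p = 65.5% (lower rounding limit of 66%) | 0.655 × 1.44 + 0.345 × 4.4 | 2.461 |
| p = 66.5% (upper rounding limit) | 0.665 × 1.44 + 0.335 × 4.4 | 2.432 |

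None gives 2.49. With weights that sum to 100%, 2.49 needs p = (4.4 − 2.49)/(4.4 − 1.44) = 64.5%, a figure the plan does not use.

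**2. Check against the head counts.** 7,237 − 4,776 = 2,461 non-participants, and 2,461/7,237 = 34.0%. Expected interval cancers: 4,776 × 1.44/1000 = 6.88, plus 2,461 × 4.4/1000 = 10.83, total 17.71. Then 17.71/7,237 = 2.447 per 1000. A rate of 2.49 would mean 18.02 cancers.

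**3. Which rate matches the stated N.** Pooled-variance z formula, one-sided, four controls per intervention woman:

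n = [1.645 √(1.25 p̄(1 − p̄)) + 0.842 √(pT(1 − pT) + pC(1 − pC)/4)]² / (pC − pT)², with p̄ = (pT + 4pC)/5.

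- pT = 0.00249: p̄ = 0.004018; n = (0.11634 + 0.05035)² / 0.00191² ≈ 7,617. That is 380 (5.3%) above 7,237. Power at the stated N is 78.0%.
- pT = 0.002446: p̄ = 0.004009; n = (0.11621 + 0.05004)² / 0.001954² ≈ 7,239. Power at the stated N is 80.0%.
- pT = 0.0024464 (unrounded): n ≈ 7,243, within 0.1% of 7,237.

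Solved backwards, n = 7,237 corresponds to 2.4458 per 1000, that is, 66.0% participation.

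**4. Sensitivity to the method.** The plan does not name the PASS test option, so other formulas were tried (one-sided 5%, 80% power, 1:4).

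| Method | n at 2.49 | n at 2.446 | Rate giving exactly 80% power at the stated N |
|---|---|---|---|
| Pooled z | 7,617 | 7,239 | 2.4458 |
| Arcsine | 7,131 | 6,762 | 2.502 |
| Unpooled z | 6,066 | 5,725 | 2.620 |

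Exact enumeration at 7,237 + 28,948, one-sided 5%: the uncorrected chi-square test has 78.7% power at 2.49 and 80.6% at 2.446; the likelihood-ratio test has 80.7% and 82.5%.

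Only the pooled formula gives 7,237 from a rate that the plan's inputs produce. The arcsine formula gives 7,237 at neither rate.

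**The case against.** The strongest reply is that nothing in the trial depends on the slip. The figures that govern conduct (66%, 4,776, 7,237, 28,948 and the total of 36,185) agree with each other. The primary comparison in Part 7, section 9 uses observed proportions, so 2.49 enters no analysis. The gap is 0.044 per 1000, about 0.3 expected interval cancers in 7,237 women (18.02 against 17.71). It also errs on the cautious side, since 2.49 implies a smaller difference from control (1.91 per 1000) than the inputs do (1.95). Under the arcsine formula, the stated N gives 80.5% power even at 2.49.

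Most of this stands. There is no shortfall in the trial, and the 78.0% and the 380 extra women apply only if 2.49 were really the target. The likelihood-ratio result is weak support for 2.49, because that test's actual size here is about 5.3%. What the reply does not do is make 2.49 follow from 66%, 1.44 and 4.4: that mismatch is independent of any test. Nor is it rounding, as 2.446 rounds to 2.45.

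The 33% should be kept apart from the 2.49, because using 33% lowers the rate. One possible source of 2.49 is a mistyped weight, since 0.66 × 1.44 + 0.35 × 4.4 = 2.490. That is a guess, but it would point to a typing error and not to a different design assumption.

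**Conclusion.** The concern holds. The printed rate is wrong on the plan's own inputs: 2.446 per 1000, not 2.49. The non-participation share should read 34%, not 33%. These are two separate slips. Both conclusions rest only on figures in section 7 and on weights that sum to 100%.

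The consequence is small. Under the pooled formula the difference is worth about 2 points of power, and the stated sample size is right for the stated assumptions. That N was calculated from about 2.446 is likely but remains an inference, since the PASS output and test option are not in the documents. It is worth correcting because the only power statement for the primary outcome cannot be reproduced from the text as it stands.

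**What to change.** First check the stored PASS run for the intervention rate that was entered. If it was about 2.446, then in Part 7, section 7:

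- replace 2.49 per 1000 by 2.446 per 1000 in both places, keeping three decimals because 2.45 would give a pooled n of 7,273;
- replace 33% by 34%;
- in the sentence on PASS, name the test option used (for example, the pooled z-test), so that N and power can be reproduced.

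Leave 7,237 + 28,948 = 36,185 as it is. If the run did use 2.49, the participation assumption behind it differs from the stated 66%, and the two must be reconciled before the text is changed.

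If the run used about 2.446, the cost is a few words: no extra participants and no change to the test, alpha or analysis.

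### Tumour size and, as it reads, stage are compared per detected tumour with no stated tumour set or window; early extra MRI finds can flatter a first-round comparison, and no per-woman rate of advanced cancer is planned

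*Combined protocol and SAP*

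**What the plan says.** Part 7, section 9 (Outcome analysis) makes the interval-cancer proportion the primary comparison and adds that "Tumour size, stage and degree of the tumours will be compared between the arms". For size, "With respect to tumour size, the difference between means will be tested" by t-test, or by Mann-Whitney on medians. Stage, grade and subtype go to chi-square or Fisher's exact test, with no denominator written out. The Design paragraph of Part 7, section 6 speaks of a tumour stage distribution and lists it among the primary outcome measures; section 9 names interval cancers alone.

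The Interim analyses paragraph sets the time as "Two years after the last participant has been screened", when "the difference in the proportion of interval cancers is analysed and the tumour size and stage between both groups are compared". Part 7, section 6 says controls have "no further examination until the following screening round 2 years later", that "it might be necessary to include the screening rounds in stages", and that for each woman "the intervention in a following screening round is the same as in her first screening round". Women enrolled early may therefore already have had round 2 at the calendar point of analysis. The plan does not say whether their round-2 cancers enter the comparison.

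The only stage-stratified incidence in the plan is an output of the simulation model in section 9. It is not a trial comparison.

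**The concern.** Only a tumour has a size, so the size test is conditional on having a detected tumour, and detection is what the intervention changes. Stage is conditional in the same way if it is read, as it most naturally is, as a property of the tumours. Only women with a negative mammogram are randomised. Before round 2, control tumours are therefore interval cancers, while the MRI arm holds interval cancers plus MRI-detected tumours. Any early tumour that MRI adds, beyond those it moves out of the interval, enlarges the denominator in one arm only. The advanced share and mean size then fall although no advanced cancer has been prevented.

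The plan accepts that such tumours may exist. Part 7, section 6 gives overdiagnosis as a reason for the parallel-group design, and the model in section 9 includes preclinical duration. Part 4, section 1 names staging among the questions that earlier studies left open and that the randomised design should help answer.

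**Working it through.** **Inputs.** From Part 7, section 7: 7,237 and 28,948 women; control interval rate 4.4/1000; rate with MRI 1.44/1000 ("we also expect that the proportion of interval cancers decreases to 1.44 per 1000 screening examinationss"); participation 66%; 8.0 cancers/1000 in all, 45% of them screen-detected. From Part 2, section 3: stage III-IV in 12% + 15% = 27% of interval cancers and 4% + 6% = 10% of screen-detected ones. From the overdiagnosis paragraph before Part 7, section 12: 8%.

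**The plan's own figure.** MRI-arm interval rate = 0.66 x 1.44 + 0.34 x 4.4 = 2.446/1000. The pooled two-proportion formula (one-sided 5%, 80% power, 1:4) then gives 7,243, which reproduces 7,237. The printed 2.49/1000 gives 7,617. Nothing below depends on this difference.

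**No extra tumours.** Moved to MRI detection: 4.4 - 2.446 = 1.954/1000. Stage III-IV per 1000 women: control 4.4 x 0.27 = 1.188; MRI arm 2.446 x 0.27 + 1.954 x 0.10 = 0.856. The per-woman ratio is 0.72. Both arms have 4.4 tumours/1000, so the ratio of shares is also 0.72 and there is no artefact.

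**Extra yield x per 1000 randomised.** The documents give none, so a range is used:
- 8% overdiagnosis applied to MRI-detected tumours: 1.954 x 0.08/0.92 = 0.17.
- Assumed: half or all of the next round's 8.0 x 0.45 = 3.6/1000 mammography cancers brought forward among participants: 0.66 x 0.5 x 3.6 = 1.19, or 0.66 x 3.6 = 2.38.

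**Stage, no reduction in interval cancers.** With a fraction s of the extras in stage III-IV, the MRI-arm share is (1.188 + x s)/(4.4 + x), against 27% in controls. Rejection rates favouring MRI come from 300,000 simulated trials per row (chi-square, stage III-IV against the rest). Two-sided means the favourable tail of a 5% test. In the last column, round-2 mammography cancers (10% stage III-IV) are added to both arms, with x fewer in the MRI arm; the per-woman ratio through round 2 is (1.188 + x s + (3.6 - x) x 0.10)/1.548, where 1.548 = 1.188 + 0.36.

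| x | s | MRI-arm share | First round, one-sided / two-sided | With round 2, one-sided (per-woman ratio) |
|---|---|---|---|---|
| 0 | - | 27.0% | 5% / 2% | 5% (1.00) |
| 0.17 | 0 | 26.0% | 6% / 3% | - |
| 1.19 | 10% | 23.4% | 11% / 6% | 5% (1.00) |
| 2.38 | 10% | 21.0% | 20% / 12% | 5% (1.00) |
| 1.19 | 0 | 21.3% | 17% / 10% | 8% (0.92) |
| 2.38 | 0 | 17.5% | 37% / 25% | 12% (0.85) |

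If the extras are all early and are not offset by fewer round-2 cancers, the one-sided rates after adding round 2 are about 11% and 21%, with a per-woman ratio of 1.00.

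**Stage, with the plan's interval reduction and s = 10%.** Ratio of shares: (0.856 + 0.119)/5.588/0.27 = 0.65 and (0.856 + 0.238)/6.776/0.27 = 0.60. The per-woman ratio through round 2 is (0.856 + 0.36)/1.548 = 0.79 at either yield.

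**Size.** The MRI-arm mean falls by x/(4.4 + x) of the size gap between the extras and the other tumours: 4%, 21% and 35% at the three yields. The documents give no tumour sizes, so this cannot be turned into millimetres.

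**The case against.** **The only excess tied to a document figure is negligible.** This stands. The sample size holds cancers at 8.0/1000, the 8% figure gives 0.17/1000, and the plan expects overdiagnosis no higher than in current screening. The yields of 1.2 and 2.4 are assumptions, and 2.4 needs MRI to bring forward every next-round mammography cancer among participants.

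**All-early extras are not a null case.** A reader might take 17% and 37% as false-positive rates. For cancers brought forward from round 2 they are not: some of those cancers would have been stage III-IV at round 2, so finding them early is a real benefit (0.92 or 0.85). The two figures are false-positive rates only for extras that would never have surfaced as advanced.

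**Counting round 2 may remove the problem.** It does for brought-forward cancers with a 10% advanced share. It does not for extras that nothing offsets. The plan does not say whether round 2 counts.

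**The test examined is a stand-in.** Section 9 names neither a stage III-IV split nor a direction for stage; one-sided alpha appears only in the sample size. The two-sided figures are therefore given alongside.

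**Existing checks cover it.** In part. The plan reports MRI yield and compares total tumours with interval cancers, but this is not stage-specific, names no test and corrects nothing. A one-sided 5% test on totals would show the excess in about 38% of trials at 1.2 and 80% at 2.4. Stage counts over the known numbers randomised would give the per-woman rate directly, but the plan does not commit to reporting it.

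**Conclusion.** The point holds in limited form. Size is certainly compared among detected tumours and stage very probably is; the tumour set and window are undefined. In a first-round comparison, early extras lower the MRI arm's advanced share and mean size without lowering its rate of advanced cancer per woman. The distortion is absent if MRI only moves tumours out of the interval and trivial at the plan's overdiagnosis figure. At assumed yields of 1.2 or 2.4 per 1000 with 10% advanced, the false-positive rate is about 11% or 20% one-sided. It persists after round 2 only for extras not offset there.

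A reader might infer that the trial's main result is biased. The documents do not support that: the interval-cancer comparison uses all women randomised and is unaffected. Nor do they establish that the stage test will mislead in practice, because the extra yield is unknown and the stage denominator is not written out. This is a cheap improvement to a comparison that section 9 does not treat as primary. Confidence is medium.

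**What to change.** In Part 7, section 9 (outcome analysis and Interim analyses), state which tumours enter the size and stage comparisons, and define the window per woman instead of by calendar date. Add stage III-IV cancers (or cancers above a fixed size) per 1000 women randomised, by intention to treat, as an estimate with a 95% confidence interval, reported twice:

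1. From randomisation to just before the round-2 examination.
2. With round-2 mammography-detected cancers added in both arms once linked. List round-2 MRI-only cancers separately, since they can arise only in the MRI arm.

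Keep the tumour-level size, stage, grade and subtype comparisons, labelled descriptive.

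The cost is SAP wording; linkage to later rounds is already described in Part 7, section 6. There are three drawbacks:
- Events are few. Report (1) expects about 0.856 x 7.237 = 6 against 1.188 x 28.948 = 34, ratio 0.72, 95% CI about 0.31 to 1.69. It estimates and does not confirm.
- Report (1) can understate MRI if brought-forward cancers include advanced ones. With 10% advanced and no true effect through round 2, it gives (1.188 + 0.119)/1.188 = 1.10 or (1.188 + 0.238)/1.188 = 1.20, where report (2) gives 1.00. Both reports are therefore needed.
- Report (2) waits for round-2 data, and Part 1, item 6 reports funding as complete only for the first round.
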